## Interaction with Other Medicinal Products and Other Forms of Interaction

### Effect of Other Medicinal Products on SZC

As SZC is not absorbed or metabolised by the body, there are no expected effects of other medicinal products on the pharmacological action of SZC.

### Effect of SZC on Other Medicinal Products

As SZC is not absorbed or metabolised by the body and does not meaningfully bind other medicinal products, there are limited effects on other medicinal products.

SZC can transiently increase gastric pH by absorbing hydrogen ions that can lead to changes in solubility and absorption kinetics for co-administrated drugs with pH-dependent bioavailability. Therefore, SZC should be administered at least 2 hours before or 2 hours after oral medications with clinically meaningful gastric pH dependent bioavailability.

Examples of drugs that should be taken 2 hours before or after SZC/placebo to avoid possible raised gastric pH drug interactions are listed in [Table 7](#).

**Table 7 Examples of Drugs that Should be Taken 2 hours Before or After SZC/Placebo to Avoid Possible Raised Gastric pH Drug Interactions**

Class of Drug	Drugs
Aazole antifungals	Ketoconazole, itraconazole, posaconazole
Anti-HIV drugs	Atazanavir, nelfinavir, indinavir, ritonavir, saquinavir, raltegravir, ledipasvir, rilpivirine
Tyrosine kinase inhibitors	Erlotinib, dasatinib, nilotinib

HIV, human immunodeficiency virus; SZC, Sodium zirconium cyclosilicate.

SZC/placebo can be co-administered without spacing of dosing times with oral medications that do not exhibit pH-dependent bioavailability.

In a clinical drug-drug interaction study conducted in healthy subjects, co-administration of SZC with amlodipine, dabigatran, clopidogrel, atorvastatin, furosemide, glipizide, warfarin, losartan, or levothyroxine did not result in clinically meaningful drug-drug interactions. No dose adjustments or separation of the time of dosing are required for these drugs.

In another drug-drug interaction study in healthy volunteers, co-administration of SZC 15 g with tacrolimus 5 mg resulted in a decreased tacrolimus area under the concentration-time curve and maximum observed concentration by 37% and 29%, respectively. Therefore, tacrolimus should be taken at least 2 hours before or after SZC/placebo. In the same study, co-administration of SZC and cyclosporin did not show a clinically meaningful interaction.

See [Appendix D](#) for drug interactions for lisinopril and valsartan.

### **6.5.2      Rescue Medication**

Rescue therapy for controlling hyperkalaemia is defined as any short-term (24 to 48 hours) therapeutic intervention during the run-in and maintenance phases, that is considered necessary as per the investigator's judgment and in accordance with local practice patterns to reduce S-K in the setting of an AE of severe hyperkalaemia. Rescue therapy is recommended

in general if S-K > 6.0 mmol/L unless otherwise specified in the protocol (see Section 6.6.4). Rescue therapy may include, but is not limited to, insulin/glucose, beta adrenergic agonists, sodium bicarbonate as well as dialysis, or other forms of renal replacement treatments, and other potassium binders including SPS, CPS, patiromer sorbitex calcium (Veltassa®) given for short-term control of severe hyperkalaemia. SZC/placebo must be temporarily discontinued while rescue therapy is administered.

All potassium binders other than SZC are considered restricted medications and can be used only for short-term rescue. They must not be used for chronic treatment during the study. Any participant who receives chronic treatment with potassium binders other than SZC/placebo must be discontinued from SZC/placebo study intervention.

Rescue medication for hyperkalaemia will not be provided as part of study medications.

### 6.5.3 COVID-19 Vaccination

COVID-19 vaccination of participants during the study is permitted as per national/local guidelines and provided the vaccine is licensed by country health authorities including emergency use authorisation by the FDA or similar authorisation by other regulatory agencies. The specific vaccine used (brand name) and each dose administered after enrolment should be recorded as concomitant medication. Adverse events suspected of being related to vaccinations should be reported as for any other AEs. Vaccines which are still in development, ie, in study, not yet approved, are not permitted.

## 6.6 Dose Modification

The investigator should rely primarily on local laboratories to make rapid or urgent decisions regarding clinical management. This includes monitoring of electrolytes (eg, S-K), renal function (eg, S-Cr), and other parameters that may be needed for appropriate CKD clinical management as per investigator's discretion.

The S-K and S-Cr samples collected and analysed by local laboratory as per the SoA (Section 1.3) or as part of routine clinical practice can also be used to adjust doses of SZC/placebo and lisinopril/valsartan.

During the run-in and maintenance phases, SZC/placebo can be titrated in the range 5 g QOD to 15 g QD. Lisinopril overall dose range/titration steps for this study are 5, 10, 20, or 40 mg QD; valsartan dose range/titration steps are 40, 80, 160, or 320 mg QD (see Table 8). In case of valsartan shortage, see Appendix E for irbesartan information. Temporary discontinuations of SZC/placebo or lisinopril/valsartan are permitted as part of the dosing regimen.

If at any point in the study lisinopril/valsartan treatment is reduced or temporarily discontinued, the investigator should make every effort to restart and maximise the dose of these agents once the cause of the reduction or discontinuation has resolved.

Instructions for dose modification and monitoring and management of S-K during the study are provided in the subsections below.

#### **6.6.1 Monitoring Lisinopril/Valsartan Titration During the Run-in and Maintenance Phases**

Anytime during the run-in and maintenance phases, if lisinopril/valsartan doses are increased (or decreased or discontinued because of hyperkalaemia), participants will be called for additional local laboratory S-K sampling after 2 weeks, or earlier, as per investigator's judgment. This includes dose changes that occur during scheduled study visits and during unscheduled visits corresponding to usual clinical care. This aligns with KDIGO 2020 Clinical Practice Guideline for Diabetes Management in CKD ([KDIGO 2020](#), Practice Point 1.2.2), which indicates that changes in S-K, S-Cr, and blood pressure should be monitored within 2 to 4 weeks of initiation or increase in the dose of an ACEi or ARB, and earlier laboratory monitoring may be indicated for participants at high risk of hyperkalaemia due to low eGFR, history of hyperkalaemia, or borderline high S-K concentration. [Appendix C](#) provides instructions for the use of SZC/placebo to manage abnormalities in S-K levels found in such visits.

All local S-K values that trigger either an SZC/placebo or lisinopril/valsartan dose modification should be specified in the clinical record. If lisinopril or valsartan doses need to be reduced or discontinued for reasons other than abnormalities in S-K, the reason should also be recorded (eg, rise in S-Cr > 30%, low blood pressure, AE).

#### **6.6.2 Lisinopril/Valsartan Dosing Upon Entry to and During the Run-in Phase**

Upon entering the run-in phase:

- Participants who are not on ACEi or ARB therapy will be started on lisinopril or valsartan on the first day of the run-in phase at the starting dose (STEP 1) indicated in [Table 8](#). The choice of drug class is per investigator judgment.
- Participants who are on other ACEi or ARB therapy at the starting daily dose will be changed to lisinopril or valsartan on the first day of the run-in phase at the starting dose (STEP 1) indicated in [Table 8](#), keeping the same drug class.
- Participants who are on other ACEi or ARB therapy with daily doses in the mid-range or at maximum will be changed to lisinopril or valsartan on the first day of the run-in phase, keeping the same drug class, following the RAASi dose equivalence guidance in [Appendix B 1](#) and [Appendix B 2](#).
- Participants who are on lisinopril or valsartan will continue treatment at the same dose.

The following dose steps in **Table 8** should be used for up-titration of lisinopril and valsartan:

**Table 8** **Lisinopril and Valsartan Dose Titration Steps**

Dose steps (daily dose)	Lisinopril (mg) a	Valsartan (mg) a
STEP 1 – Starting dose	10 (5) b	80
STEP 2	20	160
STEP 3	40	320

a Starting dose and dose range may differ per local labels. For example, in Japan, where starting and/or maximum doses are lower than specified above, the following would apply:

- STEP 1: lisinopril 10 mg; valsartan 40 mg
- STEP 2: lisinopril 20 mg; valsartan 80 mg
- STEP 3: lisinopril 20 mg; valsartan 160 mg

b If lisinopril starting dose is 5 mg (eg, if eGFR  $\geq 10$  to  $\leq 30$  mL/min/1.73m^2, or participant is on diuretics, or per local label), stepwise increase in these cases may require an additional step: 5, 10, 20 and 40 mg. eGFR, estimated glomerular filtration rate.

As per Section 4.1.3, if temporary use of irbesartan is necessary due to local market shortage, see [Appendix E](#) for further details, including conversion information for changing from valsartan or other ARBs to irbesartan, ARB dose equivalence ranges, dose modification strategy for irbesartan, and other prescribing information about irbesartan.

### **6.6.3 Strategy for Lisinopril/Valsartan Up-Titration During the Run-in Phase Visits**

Review of concurrent drugs and dietary potassium intake should be performed in all cases of hyperkalaemia before a decision is made to reduce or withdraw lisinopril/valsartan therapy. Whenever lisinopril/valsartan is temporarily discontinued because of hyperkalaemia and these agents are already at the lowest possible dose, every effort should be made to reinitiate them as soon as possible at the investigator's discretion and following a review of concurrent drugs and dietary potassium intake. In this case starting doses of lisinopril/valsartan should be used. Suitability of lisinopril/valsartan up-titration based on other clinical parameters, such as S-Cr and blood pressure, is left to the investigator's clinical judgment ([KDIGO 2020](#)). At any step during the study if hypokalaemia (S-K  $< 3.5$  mmol/L) occurs, see [Appendix C](#) for further actions.

#### Visit 4 (Day 13 $\pm$ 3 days)

- If S-K is  $\geq 3.5$  and  $< 4.7$  mmol/L, and if not already on maximum dose, increase lisinopril/valsartan one step; follow 2 weeks later with a local laboratory measurement of S-K.
- If S-K is  $\geq 4.7$  and  $\leq 5.5$  mmol/L, increase SZC to 15 g QD, repeat S-K in 48 hours and follow instructions in [Appendix C](#); if lisinopril/valsartan is increased one step based on these instructions, follow 2 weeks later with a local laboratory S-K measurement.

- If S-K is  $> 5.5$  and  $\leq 6.0$  mmol/L, temporarily discontinue lisinopril/valsartan, increase SZC to 15 g QD, repeat S-K in 48 hours and follow instructions in [Appendix C](#). After 48 hours:
  - If S-K is  $\geq 3.5$  and  $< 4.7$  mmol/L, restart lisinopril/valsartan at previous dose.
  - If S-K is  $\geq 4.7$  and  $\leq 5.0$  mmol/L, restart lisinopril/valsartan at lower dose if available. If lower dose is not available, consider reinitiating lisinopril/valsartan at starting dose 2 weeks after visit or permanently discontinue lisinopril/valsartan as per investigator judgment.
  - If S-K is  $> 5.0$  and  $\leq 6.0$  mmol/L, reduce or permanently discontinue lisinopril/valsartan per investigator judgment.
  - If S-K is  $> 6.0$  mmol/L, permanently discontinue lisinopril/valsartan, continue short-term rescue therapy as per SoC.
- If S-K  $> 6.0$ , temporarily discontinue lisinopril/valsartan, increase SZC to 15 g QD, repeat S-K in 48 hours, consider short-term rescue therapy as per SoC. Per [Appendix C](#), after 48 hours:
  - If S-K is  $\geq 3.5$  and  $< 4.7$  mmol/L, restart lisinopril/valsartan at previous dose.
  - If S-K is  $\geq 4.7$  and  $\leq 5.0$  mmol/L, restart lisinopril/valsartan at lower dose if available. If lower dose is not available, consider reinitiating lisinopril/valsartan at starting dose 2 weeks after visit or permanently discontinue lisinopril/valsartan as per investigator judgment.
  - If S-K is  $> 5.0$  and  $\leq 6.0$  mmol/L, reduce or permanently discontinue lisinopril/valsartan per investigator judgment.
  - If S-K is  $> 6.0$  mmol/L, permanently discontinue lisinopril/valsartan, continue short-term rescue as per SoC.
- Follow 2 weeks after any dose adjustment with a local laboratory S-K measurement or earlier if clinically indicated.

Unscheduled visit for monitoring of lisinopril/valsartan up-titration 2 weeks after Visit 4 (or earlier if clinically indicated)

- If S-K is  $\geq 3.5$  and  $< 4.7$  mmol/L, increase lisinopril/valsartan one step (if not already maximal); follow 2 weeks later with a local laboratory measurement of S-K.
- If S-K is  $\geq 4.7$  mmol/L, follow instructions in [Appendix C](#); chosen path depending on whether SZC is at maximum dose or not.

Up-titration of lisinopril/valsartan should be continued following the above stepwise scheme until the maximum dose has been achieved.

It is generally expected to take up to 3 up-titration steps and up to 6 weeks (2 weeks for each step) for a participant to reach the maximum lisinopril/valsartan dose during the run-in phase.

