### **7.1.1.1 Procedures for Permanent Discontinuation of Study Intervention**

The following general procedures should be followed when study intervention is discontinued.

- The Investigator should instruct participants to contact the site before or at the time study intervention is stopped. A participant who decides to discontinue study intervention will always be asked about the reason(s) and the presence of any AEs.
- If at any time during the course of the study, discontinuation of lisinopril/valsartan or SZC/placebo is deemed advisable by the Sponsor for safety reasons, the study physician will promptly discuss with the principal investigator to agree on discontinuing these agents and further actions to take to ensure the participant's safety.
- With the exception of the initiation phase, the participant should attend an ED visit if any study intervention is discontinued. The ED visit should take place as soon as possible after discontinuation and can be combined with a scheduled visit, if appropriate. See the SoA (Section [1.3](#)) for data to be collected at the time of the ED visit. It is possible for a participant to have more than one ED visit (ie, if SZC/placebo or lisinopril/valsartan are discontinued at different times).
- The time and the reason for discontinuation of any study intervention will be recorded.

- Participants discontinuing study intervention should be given locally available SoC therapy, at the discretion of the investigator.

Additional procedures to be followed when a participant is discontinued from study intervention are described below for each phase of the study:

- Initiation Phase
  - If SZC is discontinued, the participant should attend a follow-up Visit 7 ( $\pm 2$ ) days after the last dose of SZC. This is the last visit in the study for the participant. See the SoA (Section 1.3) for data to be collected at the follow-up visit.
- Run-in Phase
  - If any study intervention (SZC or lisinopril/valsartan) is discontinued, the other study intervention must be discontinued. See NOTE.
  - The participant should attend an ED visit.
  - The participant should attend a follow-up Visit 7 ( $\pm 2$ ) days after the last dose of study intervention. This is the last visit in the study for the participant. See the SoA (Section 1.3) for data to be collected at the follow-up visit.
- Maintenance Phase
  - If either SZC/placebo or lisinopril/valsartan is discontinued:

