a After actions in a panel are completed: recheck S-K within 2 weeks if RAASi therapy is restarted at any dose or increased (see [KDIGO 2020](#)); otherwise, recheck S-K at investigator's discretion; and proceed as per Appendix C per new S-K values.

- b KDIGO 2020 Clinical Practice Guideline for Diabetes Management in CKD ([KDIGO 2020](#)).
- c SZC/placebo must be temporarily discontinued when rescue therapy is administered. Once rescue therapy is completed (typically within a few hours), SZC/placebo can be resumed at the maximum dose (if not already at maximum dose).
- d If S-K is  $\geq 4.7$  and  $\leq 5.0$  mmol/L, and the participant is on SZC 15 QD and a stable dose of lisinopril/valsartan, a S-K re-check at 48h and further actions may not be necessary. This decision is left to the investigator's clinical judgment.

CKD, chronic kidney disease; KDIGO, Kidney Disease: Improving Global Outcomes; PBO, placebo; QD, once daily; S-K, serum potassium; SoC, standard of care; SZC, Sodium zirconium cyclosilicate.

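### Rescue lasts 24 to 48 hours in Sections 6.5.2 and 6.6.4 but a few hours in Appendix C, so the 48-hour potassium that decides RAASi treatment after Visit 4 may be taken during or just after rescue, with little or no SZC given at 15 g

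*Protocol*

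**What the plan says.** Protocol Section 6.6.3, Visit 4 (Day 13 ± 3, run-in), deals with potassium above 6.0 mmol/L in one bullet. The site is to "temporarily discontinue lisinopril/valsartan, increase SZC to 15 g QD, repeat S-K in 48 hours, consider short-term rescue therapy as per SoC". No hold of SZC is mentioned there. With a reference to Appendix C, the bullet then sets the next step by the 48-hour potassium. Below 4.7, lisinopril/valsartan restarts at the previous dose. From 4.7 to 5.0, it restarts lower where a lower dose exists. Above 5.0 and up to 6.0, the site is to "reduce or permanently discontinue lisinopril/valsartan per investigator judgment". Above 6.0, it is to "permanently discontinue lisinopril/valsartan, continue short-term rescue as per SoC".

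Section 6.5.2 defines rescue as "any short-term (24 to 48 hours) therapeutic intervention during the run-in and maintenance phases", recommends it in general above 6.0 mmol/L, and states: "SZC/placebo must be temporarily discontinued while rescue therapy is administered".

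Section 6.6.4, Visit 7, sets out a full order for participants above 5.5 mmol/L on a mid-range or maximum RAASi dose: pause both agents, give rescue for 24 to 48 hours, restart SZC/placebo, then raise it.

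Appendix C footnote c repeats the hold but gives a different length: "Once rescue therapy is completed (typically within a few hours), SZC/placebo can be resumed at the maximum dose".

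Section 7.1.1.1, run-in phase, gives the consequence of a permanent stop: "If any study intervention (SZC or lisinopril/valsartan) is discontinued, the other study intervention must be discontinued". The follow-up visit is then the participant's last.

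**The concern.** The 48-hour potassium after Visit 4 is a decision sample. It separates participants who resume RAASi therapy from those who are reduced and those who leave. Section 6.6.3 reads as though the sample tests potassium after two days with SZC raised to 15 g. If rescue is given and SZC is held for the length that Section 6.5.2 defines, it may instead test potassium during or just after acute treatment, with little or no SZC given at the raised dose. Two sites reading different pages for rescue length could then decide on samples that mean different things. At stake are safety management at a high potassium level and consistency in who leaves during run-in and on what RAASi dose the others continue.

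**Working it through.** The documents give no figure to reproduce, so the check compares the passages and applies one subtraction.

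**1. Rescue length.** Three places state it:
- Section 6.5.2: 24 to 48 hours, explicitly covering run-in and maintenance.
- Section 6.6.4, Visit 7: 24 to 48 hours.
- Appendix C footnote c: typically a few hours.

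Nothing in the available text reconciles the third with the first two.

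**2. SZC during rescue.** Section 6.5.2 and footnote c both require a hold. The Visit 4 bullet gives the raised dose and the 48-hour recheck without the hold.

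**3. Time left for SZC before the sample.** Let R be the rescue length in hours and assume that rescue starts at Visit 4. Then the time left is 48 − R, and the share of the interval under hold is R/48.
- R = 3 (one reading of a few hours, an assumption): 48 − 3 = 45 h left; 3/48 ≈ 6% under hold.
- R = 6 (another such reading): 48 − 6 = 42 h left; 6/48 = 12.5%.
- R = 24 (lower end in Section 6.5.2): 48 − 24 = 24 h left; 24/48 = 50%.
- R = 48 (upper end): 48 − 48 = 0 h left; 48/48 = 100%.

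If rescue starts s hours after Visit 4, the sample falls inside rescue when s + R > 48, that is, when s > 48 − R. With R = 48, any delay does this. With R = 24, a delay of more than 24 h is needed.

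**4. Does the decision rule allow for this?** At Visit 4 the action depends on the potassium value, the dose available and investigator judgment. Recent rescue is not a condition. At Visit 8 (Section 6.6.4) it is. In the normal potassium range, that visit separates participants with and without rescue at Visit 7, and asks whether rescue continued in the preceding 72 hours. Above 5.0 mmol/L it again separates by rescue at Visit 7. So the protocol treats recent rescue as relevant to a similar decision in maintenance, but Section 6.6.3 is silent on it.

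**5. How likely is the overlap?** Rescue at Visit 4 is to be considered, not required. However, Section 6.5.2 recommends it in general above 6.0 mmol/L, the threshold that opens this bullet. Its stated exception refers to Section 6.6.4, not 6.6.3.

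**6. Consequence.** A 48-hour value above 6.0 leads to a permanent RAASi stop. From above 5.0 to 6.0, a permanent stop is one of two options. Under Section 7.1.1.1 a permanent stop in run-in also ends SZC and participation.

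**The case against.** The strongest reply is that the protocol does not contradict itself on the hold, and this largely stands. A reader might infer that Section 6.6.3 orders SZC to be given during rescue. It does not say so. Section 6.5.2 and footnote c agree on the hold, the bullet refers to Appendix C, and footnote c has SZC resumed at its maximum, which is the 15 g QD named at Visit 4. The omission in the bullet is a gap in clarity.

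On duration, the reply is that 48 hours may be a ceiling and a few hours the usual length. SAP Section 4.1.8.1 supports a ceiling for potassium binders, treating rescue as short term at up to 2 days. That softens the clash but does not remove it: Sections 6.5.2 and 6.6.4 give a range that starts at 24 hours, and a rescue of the permitted maximum still fills the decision interval.

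Four further inferences are tempting and are not supported:
- *A fixed number of SZC doses before the sample.* The documents give none. Any count depends on assumed dose times and on when rescue starts. Participants have also been on SZC since Day 1, so the sample is not from an untreated state.
- *A flaw in the estimand.* The population in Section 9.4.2.1 is defined by normokalaemia after the 3-month run-in, tested at Visit 6a, and not by this sample.
- *Bias between arms.* Run-in is open-label, single-arm and before randomisation.
- *A wrong verb in the branch above 5.5 and up to 6.0 mmol/L.* That bullet tells the site at 48 hours to continue rescue without having started it, but it sends the site to Appendix C, whose chart is not in the text available here. Whether this is an error cannot be settled.

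**Conclusion.** The point holds as an inconsistency in rescue length with a consequence for one decision. Sections 6.5.2 and 6.6.4 say 24 to 48 hours and Appendix C says typically a few hours. Where rescue of the length in Section 6.5.2 starts at Visit 4, SZC is held for 24 to 48 of the 48 hours before the sample that decides RAASi restart, reduction or permanent stop, and Section 6.6.3 does not allow for that.

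The scope is limited. It concerns only participants above 6.0 mmol/L at Visit 4 who receive rescue, and the documents do not say how many there would be. An automatic exit follows only if potassium is still above 6.0 at 48 hours. The effect is on safety handling and on consistency of run-in exits, not on the randomised comparison. The conclusion assumes that the unseen Appendix C chart does not itself settle rescue length and sample timing. No view is taken on which clinical rule is right.

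**What to change.** Reconcile Section 6.5.2, Section 6.6.3 (Visit 4), Section 6.6.4 (Visit 7) and Appendix C footnote c so that they agree on three things: how long rescue lasts, what happens to SZC while it is given, and how the 48-hour decision sample is timed or interpreted relative to the end of rescue and the restart of SZC. The Visit 4 bullet should carry or cross-reference the hold. The sponsor's clinical team should choose the rule. The sponsor should also check the wording on continuing rescue in the branch above 5.5 and up to 6.0 mmol/L against the Appendix C chart, and change it only if the chart does not start rescue there.

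The cost is wording in four places, by amendment or clarification letter, with no new procedure required by the reconciliation itself. The SAP records that the study was terminated early, so an amendment may have no further use in this trial. In that case the point should be kept in mind when run-in exits are described in the study report, and corrected before the algorithm is reused.
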